3. SUBJECT SELECTION AND WITHDRAWAL

- a) **Number of subjects:** 20
- b) **Gender of subjects:** Any (goal is consecutive recruitment)
- c) **Age of subjects:** Adult
- d) **Racial and Ethnic Origin:** Any (goal is consecutive recruitment)
- e) **Inclusion Criteria:**
- i. Adult (18 years or older) patients able to participate in the consent process
 - ii. Have undergone colon or rectal resection within 30 days
 - iii. CT-proven abdominopelvic fluid collection > 3 cm in average diameter
 - iv. Surgeon has determined patient is clinically stable for unaccompanied transport to the MRIRC for image acquisition
- f) **Exclusion Criteria:**
- i. Contraindication to MRI (eg. Implant or other medical device)
 - ii. Pregnant women, prisoners, and cognitively impaired persons
 - iii. Claustrophobia preventing MRI acquisition
 - iv. Not clinically stable to be transported unaccompanied to the MRIRC for image acquisition
 - v. MRI acquisition will delay percutaneous drainage
- g) **Vulnerable Subjects/Subject Capacity to provide consent:** Otherwise eligible subjects must retain capacity to consent to DW-MRI in order to be considered for the study.
- h) **Location where research is to be conducted (building, floor, clinic/suite number):** CUMC and the MRIRC
- i) **Describe how subject's primary treating physician will be notified of, and if appropriate, involved in the proposed research:** All UCMC surgical faculty who perform colon or rectal resection will be briefed on the study details. The surgeon study team will not have direct involvement in DW-MRI acquisition and image analysis. The radiology study team will not have direct involvement in clinical care or clinical decision-making.
- j) **As applicable, the coordination of any interdepartmental faculty, and where necessary, the inclusion of those faculty as participants:** All UCMC surgical faculty who perform colon or rectal resection will be briefed on the study details. The surgeon study team will not have direct involvement in DW-MRI acquisition

and image analysis. The radiology study team will not have direct involvement in clinical care or clinical decision-making.

- k) **Method of subject identification and recruitment.** Adult patients who have undergone a colon or rectal resection at the University of Chicago Medicine within 30 days and have developed a CT-proven abdominopelvic fluid collection > 3 cm in average diameter, for which the surgeon determines based on best clinical practice that percutaneous drainage is indicated, will be eligible for inclusion in the study. These patients will be reasonably on the colon and rectal surgery census, the surgical oncology patient census, or the resident acute care surgery census or in any of these complimentary ambulatory settings. In the event a patient otherwise meets criteria but the surgeon has determined that percutaneous drainage is not indicated, they will not be eligible for inclusion in the study. If, due to nonresolution or worsening clinical status, the surgeon later decides that percutaneous drainage is appropriate, that patient will only then become eligible for the study.
- l) **Describe plans for remuneration to subject, as applicable:** N/A
- m) Informed consent process
[Click here for an *Informed Consent Checklist* template](#)
- n) **Waiver of consent/waiver of authorization (as applicable):** N/A
- o) **Method of withdrawing subjects following completion of study:** N/A – single point intervention (DW-MRI acquisition)
- p) **Method of withdrawing subjects before completion (i.e., early termination):**
 - i. In the event that a subject consents for the study and only after this discloses extreme claustrophobia or metal implant which would preclude them from DW-MRI, this will be considered a screening failure and these patients will not be included on any analysis.
 - ii. If the subject's clinical status changes after initial screening such that they are no longer safe for transport to the MRIRC for image acquisition, or if it is the case that MRI acquisition will actually delay percutaneous drainage, the subject will be considered a screening failure and will not be included in the analysis.
- q) **Method of collecting data and follow-up on subjects who have been withdrawn:** N/A

5. STUDY PROCEDURES

- a) Please see patient flow (**Figure 2**) as well as study design.
- b) This is a single point intervention (DW-MRI acquisition) within the context of a usual clinical care pathway. The results of the DW-MRI will not be utilized for clinical decision making for the subjects in the study. Primary output measures are ADC threshold to discriminate sterile from infected post-operative fluid collections which may be used to guide a larger prospective study.
- c) Labs, diagnostic testing, post-operative visits, and further intervention will be at the discretion of the surgeon based on usual best clinical care and not directly born of the study intervention (i.e. not research related).
- d) **Methods and procedures:** See 'MRI acquisition' above under Study Design.

- e) **Scales/assessments:** None
- f) **Examinations:** None related to this single-point intervention
- g) **Questionnaires:** None
- h) **Labs to be conducted:** None related to this single-point intervention
- i) **Plan for unscheduled visits:** None related to this single-point intervention
- j) **Contact between study visits:** None specifically research related. Patients will undergo usual post-operative care.
- a) **Future contact regarding research studies:** None specifically research related. Patients will undergo a routing post-operative visit or visits at the discretion of their treating surgeon.

Refer to [SCHEMA](#) in Appendix B.

6. STATISTICAL PLAN AND CONSIDERATIONS

For assistance with plans for biostatistics in this research, please visit the Department of Health Studies at www.health.bsd.uchicago.edu.

Discuss the following in detail:

- a) **Sample size determination**— Our sample size of twenty (20) patients is justified in that we believe recruitment can be accomplished within 9 months. True pace of recruitment/refusal/crossover will drive the timeline of a future full-scale study, and may influence inclusion/exclusion criteria of the full-scale study.
- b) **Power analysis or considerations**— Results of the study (i.e. the calculated ADC threshold) will be used to drive a power analysis for a future larger study to determine if addition of DW-MRI to the care paradigm results in clinically meaningful improvement in care.
- c) Statistical methods: **DW-MRI differentiation metrics and abscess characterization**
 - *Qualitative analysis:* The collection will be presented to two separate radiologists who will be blinded to patients' history, laboratory results, findings from other imaging modalities, and final diagnosis. They will independently review the MR images for detection of collections (T2-weighted images together with diffusion-weighted images and ADC maps (T2 + DW-MRI). ADC maps will be generated for each patient using a home grown software. Each radiologist will assign a score from a five-point scale (1 = no abscess; 2 = probably not an abscess; 3 = equivocal; 4 = possible abscess; 5 = definite abscess) based on the level of confidence in the diagnosis for each review session. A score of 4 or 5 will be considered as positive for diagnosis of abscess for each case.
 - *Quantitative analysis:* Following qualitative analysis, the same two radiologists independently will measure ADC of the collections in each patient on ADC maps. Mean and 10th percentile ADC values will be computed by placement of region of interest (ROI) on ADC maps using DW images as guide. Each ROI will be placed in the center of the

collection over the darkest pixels on ADC maps keeping size as large as possible and avoiding the volume averaging from the surrounding tissue. The reference standard for the diagnosis of abscess will be based on the analysis of aspiration fluid from the collection. *Statistical analysis:* For statistical analyses, a software package (SPSS 11.0 for Windows; SPSS Inc., Chicago, IL, USA) will be used. Sensitivity and specificity of each review session for each radiologist will be calculated. McNemar's test will be used for multiple comparisons of sensitivity of different review sessions. Confidence score of each review session will be compared using Wilcoxon-signed rank test. Two-tailed Student's *t* test will be used for comparison of ADC values. A two-tailed *p* value of less than 0.01 will be considered to indicate a statistically significant difference. Simple κ coefficients will be used to assess interobserver agreement for confidence score and ADC measurements. An ROC curve will be constructed for ADC values, and area under the curve measured the overall ability of ADC in differentiation of abscess from non-infected collections.

d) Subject Population(s) for Analysis

- *All-imaged population:* Any subject who underwent DW-MRI in the post-operative setting after identification CT-proven intrabdominal collection > 3 cm in average diameter, whom the surgeon determines based on best clinical practice that percutaneous drainage is indicated.

e) If any Intent to Treat Analysis will be done on subjects withdrawing before completion or those who remained in the study but withdrew from intervention, please describe in detail: Not applicable

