 - f) **Rationale for research design and population**— The novelty of the proposed research project is that it seeks to broaden applicability of a proven but rarely used method, DW-MRI, to discriminate sterile or benign from infected abdominopelvic fluid collections, in order to enhance the utilization of percutaneous drainage in the post-operative setting after colorectal resection (Oto). Ability to streamline a limited MRI protocol to efficiently obtain diffusion weighted imaging of the abdominal cavity will be key to applying this methodology into daily practice. Secondly, it is not known whether DW-MRI can effectively discriminate specifically *post-operative* sterile collections from abscesses. This is one of the primary aims of this pilot study and will be used to generate hypothesis for a full-scale study.

B. OBJECTIVES

- a) **Hypothesis-** DW-MRI is effective in discriminating sterile from benign abdominopelvic collections in the post-operative setting after colon or rectal resection with a high degree of discrimination using a defined apparent diffusion coefficient threshold.
- b) **Describe in detail the study objectives, including primary and secondary**

- a. *Objective 1.* To devise a limited abdominal diffusion-weighted imaging protocol for evaluation of intra-abdominal collections in the post-operative setting.
- b. *Objective 2.* To identify the DW-MRI characteristics of infected and sterile intra-abdominal fluid collections in the post-operative setting after colon and rectal resection, and compare and determine best DW-MRI metrics for their differentiation.
- c. *Objective 3.* To construct and demonstrate safety and feasibility of a protocol using diffusion-weighted MR imaging to guide selective percutaneous drainage of post-operative intra-abdominal abscesses after colorectal resection, and prevent drainage of sterile collections

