- f) **Primary and secondary endpoints:**
- a. Primary output measures are ADC threshold to discriminate sterile from infected post-operative fluid collections
- g) **Primary safety endpoints (must be measurable):** Not applicable

- h) **Rationale for study design:** The results of this pilot trial will form the basis of the R21 grant that our team is planning to submit in 2018. The data will help us to identify potential limitations of DWI in differentiation of abscess from non-infected collections allow us to determine the appropriate cohort size for the NIH grant. Based on the correlation with DWI and clinical data, we will explore and suggest novel acquisition and analysis methods for quantitative DWI. Each exam will be limited to the collection that was already detected and localized by CT. Each exam will include a breath-hold T2-SSFSE, T1-w GRE and DWI sequence. Total scanner time per patient is expected to be under 30 minutes.

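### Section 6c takes both the mean and the 10th percentile ADC from ROIs steered to the darkest pixels; add a whole-collection contour so that Objective 2 has a measure of the whole collection to compare

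*Combined protocol and SAP*

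**What the plan says.** Under Quantitative analysis, section 6c states that "the same two radiologists independently will measure ADC of the collections in each patient on ADC maps". The metrics are defined as follows: "Mean and 10th percentile ADC values will be computed by placement of region of interest (ROI) on ADC maps using DW images as guide". The placement rule comes next. ROIs are to sit centrally, and the rule goes on: "collection over the darkest pixels on ADC maps keeping size as large as possible". Readers must also keep clear of neighboring tissue, so that partial volume does not enter. This rule governs both metrics. The section gives no minimum coverage, no slice rule, no number of ROIs per collection and no contour of the whole collection.

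Two other places depend on these measurements. Objective 2 (section 1B) is to "compare and determine best DW-MRI metrics for their differentiation". Section 2f states: "Primary output measures are ADC threshold to discriminate sterile from infected post-operative fluid collections". Section 6b then carries the threshold into the power analysis of a later study.

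Section 1A(c) explains why the post-operative setting is an open question. The earlier study of abscess and ascites did not include such collections, and inflammatory fluid or blood might weaken the separation that it found.

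**The concern.** The ROI is positioned by the quantity that it is meant to measure. In uniform fluid this matters little. In a mixed collection, the reader is steered toward the lowest values before either summary is computed. The result is described as the ADC of the collection, but it describes a selected part of it.

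Mixed sterile collections are a plausible form of the problem raised in section 1A(c). If only a darkest-region measurement is taken, the pilot cannot show whether poor discrimination comes from the fluid or from where the ROI was put. Objective 2 also cannot say whether a summary of the whole collection would do better or worse, because none is measured.

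The three parts of the rule (center, darkest, as large as possible) also pull apart when the dark pixels are few or off-center. Two readers could both follow the text and draw different regions.

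**Working it through.** The documents give no bias, coverage or within-collection figure, so there is no stated result to reproduce. The check is whether the rule fixes a direction, and how the size varies with what is not stated.

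**Inputs from the documents** (Appendix E, Figure 1 caption, observer 1, x10^-3 mm2/s): abscess 1.17 ± 0.42, non-infected ascites 3.57 ± 0.68, cut-off 2.00. Under normality, Φ((2.00 − 1.17)/0.42) = 97.6% of abscesses fall below the cut-off and Φ((3.57 − 2.00)/0.68) = 99.0% of ascites fall above it. That broadly fits the separation cited.

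**Assumptions (not in the documents):** a sterile collection is fluid voxels at 3.57 plus a share f of low-ADC voxels at 1.17, the abscess mean standing in for blood or debris. Voxel SD s is 0.2, with 0.4 as a check. The ROI covers a fraction g of the collection and takes strictly its darkest voxels, which is the upper bound of the effect.

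**Percentile.** Under strict selection, the lowest 10% of the ROI is the lowest 0.10 × g of the collection. The ROI's 10th percentile is therefore the collection's 8th, 5th or 2.5th percentile at g = 0.8, 0.5 or 0.25.

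**Mean, uniform collection (f = 0).** The shift is −s·φ(z_g)/g, where z_g is the normal quantile at g. That is −0.35, −0.80 and −1.27 voxel SDs at the three coverages.

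**Mean, mixed collection (f = 0.3, s = 0.2).**
- Whole: 0.3 × 1.17 + 0.7 × 3.57 = 2.85.
- For f < g, ROI mean ≈ [f × 1.17 + (g − f) × (3.57 − s·φ(z_q)/q)]/g, with q = (g − f)/(1 − f).
- g = 0.8: q = 0.714, φ(z_q)/q = 0.476, so (0.351 + 0.5 × 3.475)/0.8 = 2.61.
- g = 0.5: q = 0.286, φ(z_q)/q = 1.190, so (0.351 + 0.2 × 3.332)/0.5 = 2.035 (2.04 in a simulation of 400,000 voxels).

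**Simulated ROI mean / ROI 10th percentile, s = 0.2:**

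| Low-ADC share f | Whole (g = 1) | g = 0.8 | g = 0.5 | g = 0.25 |
|---|---|---|---|---|
| 0 | 3.57 / 3.31 | 3.50 / 3.29 | 3.41 / 3.24 | 3.32 / 3.18 |
| 0.1 | 3.33 / * | 3.20 / 1.34 | 2.95 / 1.17 | 2.43 / 1.04 |
| 0.2 | 3.09 / 1.17 | 2.91 / 1.12 | 2.49 / 1.03 | 1.57 / 0.94 |
| 0.3 | 2.85 / 1.08 | 2.61 / 1.05 | 2.04 / 0.98 | 1.11 / 0.89 |

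*At f = 0.1 the whole-collection 10th percentile falls in the gap between the two components and is not a stable figure.

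With s = 0.4 the pattern is the same. At f = 0.3 the mean goes from 2.85 to 2.55, 1.94 and 1.05.

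**Distance from the cited cut-off.** Ignoring voxel noise, an ROI mean of 2.00 needs a low-ADC share inside the ROI of (3.57 − 2.00)/(3.57 − 1.17) = 65.4%. The share needed in the collection is 0.654 × g: 65% at full coverage, 52% at 80%, 33% at 50% and 16% at 25%.

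**The case against.** The strongest reply is that the rule limits itself. The ROI must be central and as large as possible, and if it fills the collection both effects vanish. At 80% coverage with 30% low-ADC voxels, the mean is still 2.61. Low coverage is an assumption, and so is strict selection of the darkest voxels. This stands. It bounds the size but does not change the direction where a mixed collection is only partly covered.

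Four stronger readings are tempting, and the documents do not support them.

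- *Sterile collections will be read as abscesses and specificity will fall.* The study derives its own threshold from data read under the same rule, so crossing the cited 2.00 is not in itself an error. A shift common to infected and sterile collections would be absorbed. Only a differential shift would harm discrimination, and nothing in the documents allows it to be computed.
- *The two metrics are near-duplicates.* At f = 0.1 the ROI mean and 10th percentile are 3.20 and 1.34 at 80% coverage, and 2.95 and 1.17 at 50%. They differ and can be compared.
- *The darkest-pixel ROI is wrong and should be replaced.* A whole-collection mean can dilute a focal infected component. A whole-collection 10th percentile also reads low once low-ADC voxels exceed about 10% (1.17 at f = 0.2). Neither definition is better on the documents alone.
- *The rule is needed to match the earlier study.* The documents do not describe that study's ROI method.

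It can also be said that this is a hypothesis-generating pilot with two independent readers and a planned agreement analysis. That analysis could show where readers differ, but not a downward shift that both share. Objective 2 does not promise a whole-collection metric, so its absence is a missed comparison, not a breach of the plan.

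**Conclusion.** The concern holds in limited form. Under section 6c, an ROI that follows the darkest pixels and does not fill a mixed collection gives a mean below the collection's mean and a 10th percentile that is a lower percentile of the collection. The direction follows from the placement rule. The size cannot be settled from the documents. In the 30% mixture it runs from zero at full coverage, through 2.85 − 2.61 = 0.24 at 80%, to about 2.85 − 2.04 = 0.81 at 50% (x10^-3 mm2/s). Those figures rest on the assumed mixture, voxel SD of 0.2 and strict selection.

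What is established is that the plan has no whole-collection metric for Objective 2 to set beside the darkest-region one, in a setting where the protocol itself doubts that discrimination carries over. No loss of specificity is shown. The change is a cheap improvement to an exploratory pilot, not the repair of a fatal flaw.

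**What to change.** In section 6c:

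- Keep the darkest-pixel ROI as a separately named metric, and state how many ROIs are placed per collection.
- Add a contour of the whole collection, drawn independently by the same two readers on the b=0 diffusion images and excluding edge voxels. Compute the mean and 10th percentile from all enclosed voxels. The b=0 images share the geometry of the ADC map. The T2 images do not: section 2c gives T2 slices of 6 mm without a gap, and diffusion sections of 5 mm at a 7 mm interval.
- Include both ROI definitions in the Objective 2 ROC comparison, without presuming which is better.

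The cost is a change of wording and a few extra minutes per case on images already acquired, with no new scans or readers. The downside is more comparisons: 2 summaries × 2 ROI definitions = 4 metrics per reader instead of 2, in 20 patients. The comparison should therefore be labeled exploratory.

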- c) **Past research and/or preclinical data**—Oto *et. al.* have identified a novel method using diffusion weighted magnetic resonance imaging (DW-MRI) of abdominopelvic collections that can perfectly discriminate abscesses from ascites with a threshold apparent diffusion coefficient (ADC) of $2.0 \times 10^{-3} \text{ mm}^2/\text{s}$ (i). It is important to note this study *did not* include collections identified in the post-operative setting; it is unclear whether inflammatory fluid or presence of blood may diminish this discrimination. If the discriminatory capacity is *not* diminished, then clearly DW-MRI has great potential within the diagnosis and treatment of post-operative abscess formation in colon and rectal resection.
 - d) **Rationale for conducting this research**— Further investigation is required in order to determine whether DW-MRI is applicable in the evaluation of post-operative collections, and whether utilization of DW-MRI can enhance application of percutaneous drainage and prevent unnecessary drainage. DW-MRI is well established in the identification and management of brain abscesses. Oto *et. al.* have already demonstrated the utility of DW-MRI in discriminating abdominopelvic abscess from ascites. They compared ADC values of abscess and non-infected ascites in 58 patients. Compared to T2-weighted images alone, addition of DW-MRI images allowed for nearly 100% detection of abscesses. Further, a cutoff ADC value of $2.0 \times 10^{-3} \text{ mm}^2/\text{s}$ allows for perfect discrimination between abscess and non-infected ascites (Oto), thereby increasing the abscess detection rate (**Fig. 1** (Fig . 7 from Oto *et. al.*)) and potentially minimizing unnecessary percutaneous aspiration or drainage.
 - e) **Dose rationale and risks/benefits (as applicable)** – Not applicable

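### McNemar and Wilcoxon tests are planned between review sessions, but only one session (T2 + DW-MRI) is defined and only sensitivity is compared

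*Combined protocol and SAP*

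**What the plan says.** The Qualitative analysis paragraph of Section 6(c) has two blinded radiologists, working separately, "review the MR images for detection of collections (T2-weighted images together with diffusion-weighted images and ADC maps (T2 + DW-MRI"). Each gives a five-point confidence score per review session, and 4 or 5 counts as positive for abscess. No other image set is named for scoring.

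The Statistical analysis paragraph then plans three things by session:

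- Both accuracy measures are to be estimated, by session and by reader, with no test attached at this point.
- For comparing accuracy between sessions, one test is named, and it covers one measure: "McNemar's test will be used for multiple comparisons of sensitivity of different review sessions".
- For the five-point scores, the comparison is again between sessions: "Confidence score of each review session will be compared using Wilcoxon-signed rank test".

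Significance is set at a two-tailed p below 0.01. The Statistical Methodology row of the Study Summary repeats the session-based tests and also names no second session.

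A T2-only comparator appears once, in Section 1A(d), as a finding of the earlier abscess-versus-ascites study: "Compared to T2-weighted images alone, addition of DW-MRI images allowed for nearly 100% detection of abscesses". Objective 3 in Section 1B includes the aim to "prevent drainage of sterile collections". Section 2(f) gives the primary output: "Primary output measures are ADC threshold to discriminate sterile from infected post-operative fluid collections".

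**The concern.** McNemar's test and the signed-rank test both work on pairs: the same collection, read by the same radiologist, under two conditions. With one condition there is nothing to pair, so two of the named tests cannot be run and the reader analysis cannot show what diffusion weighting adds to the other MR images.

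The gap could also be filled badly. If a second session is improvised after the T2 + DW-MRI scores exist, its image set and order will not have been prespecified. A T2-only read that follows the full read is also open to recall.

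The second issue is that sensitivity is the only accuracy measure compared between sessions. A reader who simply calls more collections positive when shown diffusion images gains sensitivity and loses specificity. At the extreme, scoring every collection 4 or 5 gives 100% sensitivity and 0% specificity. A sensitivity-only comparison would count that as improvement, in a study motivated by needless drainage of sterile fluid.

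**Working it through.** The plan gives no power, effect size or discordance rate for these tests, and Section 6(a) justifies the 20 patients by recruitment alone. There is no figure to reproduce.

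Step 1: could anything in the text serve as the second session?

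| Candidate | Where | Why it does not serve |
|---|---|---|
| The two radiologists | 6(c) | Accuracy is per session and per radiologist, so the two are distinct; reader agreement is assigned to kappa |
| ADC measurement | 6(c), Quantitative analysis | Follows the read and yields ADC values, not a five-point score |
| CT | 6(c) | Readers are blinded to other imaging modalities |
| T1-weighted images | 2(c) | Acquired, but assigned to no read |
| T2 alone | 1A(d) | A result of the earlier study, not a procedure here |

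Defined sessions: 1. Pairs for McNemar or Wilcoxon: 0.

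Step 2: which between-session comparisons address accuracy? McNemar is limited to sensitivity. Wilcoxon compares confidence, not correctness against the aspirate. The ROC curve concerns ADC values, not sessions. Specificity is calculated but not compared.

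Step 3: scale if a T2-alone session were added. The inputs from the documents are 20 patients and two-sided 0.01. The assumptions are:

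- 12 infected and 8 sterile, borrowing the figure of up to 40% sterile that Section 1A gives for rim-enhancing collections.
- T2 sensitivity of 50%, 60% or 70%, rising to 100% with diffusion images, with no reversals.

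Let n be the number of discordant pairs, all in one direction. The plan does not name the McNemar version, so three are shown.

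| Version | Formula | Just short | Smallest n with p < 0.01 |
|---|---|---|---|
| Uncorrected | chi-square = n, 1 df | n = 6, p = 0.0143 | n = 7, p = 0.0082 |
| Exact | p = 2 × 0.5^n | n = 7, p = 0.0156 | n = 8, p = 0.0078 |
| Continuity-corrected | chi-square = (n − 1)²/n, 1 df | n = 8, p = 0.0133 | n = 9, p = 0.0077 |

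The chance of p < 0.01 is P(Bin(N, 1 − T2 sensitivity) ≥ smallest n), where N is the number infected.

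| N infected, version | T2 sensitivity 50% | 60% | 70% |
|---|---|---|---|
| 12, uncorrected | 0.387 | 0.158 | 0.039 |
| 12, exact | 0.194 | 0.057 | 0.0095 |
| 12, corrected | 0.073 | 0.015 | 0.0017 |
| 16, exact | 0.598 | 0.284 | 0.074 |

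For specificity, 6 or fewer sterile collections cannot reach 0.01 under any of the three versions, since n = 6 gives at best 0.0143. With 8 sterile, the exact test needs all 8 to change. For a 50-point gain that has probability 0.5^8 = 0.004.

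Step 4: what an interval would say. Limits are exact unconditional 95% limits for the paired difference (score ordering, nuisance parameter maximised over a grid), with Tango score limits as a cross-check.

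| Result | Difference | Exact 95% CI | Tango 95% CI |
|---|---|---|---|
| 6 of 12 infected corrected, 0 reversed | 6/12 = +50 points | 13 to 80 | 14 to 75 |
| 4 of 8 sterile corrected, 0 reversed | 4/8 = +50 points | −5 to 84 | 1 to 79 |

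**The case against.** The strongest reply is that this is a missing definition rather than an impossible analysis. Asking for a score per session implies that more than one was intended. The sentence describing the read has an unbalanced bracket, which fits lost words, and Figure 2 and the Appendix B schema cannot be seen. That limits the claim to the visible text, but does not remove it. Figure 2 is captioned and cited for project design and patient flow, and nothing points to it or the schema for reading sessions. Someone following the text still could not run the tests.

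It can also be said that no objective asks what diffusion imaging adds to T2. Objective 2 compares DW-MRI metrics, and the superiority statement in Section 7(d) is against CT. This stands in part: T2 alone is an inferred comparator, so deleting the tests is a legitimate remedy.

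On specificity, a further significance test would add little at this size, as the working shows. That supports reporting an interval, not leaving the comparison out. The link to safety in Objective 3 is weaker: the objective sets out "To construct and demonstrate safety and feasibility of a protocol using diffusion-weighted MR imaging", but Section 2(g) lists safety endpoints as not applicable, and Section 2(d) measures Objective 3 by change in management decision. The case for specificity therefore rests on the aim of sparing sterile collections and on the positivity shift that sensitivity alone cannot detect.

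Finally, the interval method matters. For 4 of 8 sterile the exact interval includes zero and the Tango interval does not, so the method has to be named in advance.

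**Conclusion.** The concern holds. As written there is one defined session and no pairs, so neither the McNemar nor the Wilcoxon comparison can be run. The only accuracy measure with a planned between-session test is sensitivity. Neither conclusion depends on an assumption.

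The power figures do depend on the assumed split, sensitivities and absence of reversals. They show only that a p < 0.01 verdict would be a poor summary with 20 patients: under the exact test with 12 infected, the chance of success is 19% at best across the scenarios shown.

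This is a defect in a secondary reader analysis and should be fixed before reading begins. It leaves intact the primary ADC threshold, the t test, the ROC curve, and each reader's sensitivity and specificity from the defined read.

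**What to change.** Before any reading starts, choose one of two courses.

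Option 1: define two sessions in Section 6(c), by the same two radiologists on images already acquired.

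- Session 1 is T2 alone, with the score locked. Session 2 is the same T2 images plus diffusion images and ADC map, which is the read already described. If T1 is shown, show it in both.
- State the case order. Either reveal the diffusion images straight after the T2 score is locked, or use separate sittings with reordered cases and a stated washout. Finish both sessions before the ADC measurement.
- For each reader, report the paired difference in sensitivity and in specificity with exact 95% confidence intervals, naming the interval method. Do not rest the conclusion on p < 0.01. If McNemar's test is kept, name the version.

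Option 2: if no read without diffusion images will be done, delete the between-session McNemar and Wilcoxon tests from the Study Summary and Section 6(c), and make no added-value claim from the reads.

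Option 1 costs plan wording and about 20 short extra reads per radiologist (2 × 20 = 40 in all), plus a washout if separate sittings are used. It needs no extra scans, patients or staff. Option 2 costs wording only.
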